6.2.2.2 Additional Secondary Efficacy Endpoints

Each of the two active treatment groups, SEL-212A and SEL-212B, are compared to placebo with regards to the following additional secondary efficacy endpoints:

- The percentage of patients who achieve and maintain reduction of sUA < 6 mg/dL for 100% of the time during Treatment Period 6
- Percentage of pre-dose sUA values ≤ 6 mg/dL during Treatment Periods 2-6 for each patient
- Pre-treatment anti-pegadricase and anti-uricase antibody formation and levels in each treatment period in the SEL-212 active treatment arms during Treatment Periods 1-6
- Percentage of patients with development of new tophi in the subgroups of tophaceous patients and in non-tophaceous patients at Baseline during Treatment Periods 1-6

- In patients with tophi at Baseline, the percentage of patients with at least PR (as best response) in overall tophus response evaluation until Day 0 of Treatment Period 4
- Change from Baseline to Day 28 of Treatment Period 6 in the subscales of Health Assessment Questionnaire (HAQ-DI), in Provider Global Assessment of Disease Activity, and in subscales of Short Form Health Survey (SF-36)
- The percentage of patients with at least 1 gout flare during Treatment Periods 1-3
- The percentage of patients with at least 1 gout flare during Treatment Periods 1-6
- Change from Baseline to Treatment Period 6 in number of swollen joints
- Length of time patients are anti-uricase antibody free or before induction of anti-uricase antibody levels above baseline in patients receiving SEL-212
- Length of time patients are anti-pegadricase antibody free or before induction of anti-pegadricase antibody levels above baseline in patients receiving SEL-212

6.2.3 Exploratory Endpoints

The exploratory endpoints of this study are:

- Levels of uricase activity in patients receiving SEL-212
- Levels of monosodium urate crystal deposits and/or total body monosodium urate crystal deposits (imaging patients only)
- Levels of inflammatory and tolerogenic biomarkers
- Changes in antibody production (anti-uricase and anti-pegadricase) in patients in the SEL-212 groups
- Gout flare incidence during Treatment Periods 4-6
- Gout flare incidence during Treatment Periods 1-3 based on self-reported weekly gout flare diary
- Gout flare incidence during Treatment Periods 1-6 based on self-reported weekly gout flare diary
- Gout flare incidence in the Treatment Periods 4-6 based on self-reported weekly gout flare diary
- Assessment of association between multiomic markers of gout and treatment effect in patients treated with SEL-212
- Comparison of immune tolerance related multiomic markers in patients on SEL-212 who developed anti-uricase and anti-pegadricase antibodies vs. those patients on SEL-212 that did not develop anti-uricase and anti-pegadricase antibodies

6.2.4 Safety Endpoints

The safety endpoints of this study are:

- Safety and tolerability of SEL-212 compared to placebo as assessed by AEs, AESI, serious AEs (SAEs), deaths, and discontinuations due to AEs
- Additional safety assessments will include review and evaluation of laboratory testing including hematology, coagulation, chemistry, urinalysis; eGFR; UACR; vital signs; immunogenicity analyses; 12-lead ECGs; and physical examination findings.

7. INVESTIGATIONAL PLAN

7.1 Overall Study Design

This study is one of two randomized, double-blind, placebo-controlled, parallel-arm trials to determine the safety and efficacy of two different dose levels of SEL-212 compared to placebo. The study will randomize approximately 140 patients with chronic refractory gout. Approximately 60% of the randomized patients will have tophi at Baseline. Patients, stratified as to the presence or absence of tophi, will be randomized in a 1:1:1 allocation ratio prior to Baseline to receive treatment with one of two dose levels of SEL-212 or placebo every 28 days for approximately 6 months in each trial (SEL212/301 and SEL-212/302). These two trials will have identical designs with respect to being double-blinded, placebo-controlled as well as identical sample sizes, inclusion/exclusion criteria, efficacy/safety assessments and timing thereof, but will be distinguished by a blinded 6-month extension in SEL-212/301 and that SEL-212/302 will include sites outside of the United States. Placebo patients in either SEL-212/301 or SEL-212/302 who complete the study, will be offered enrolment in an open-label extension study for treatment with SEL-212 (SEL-212/303). Efficacy assessments will be conducted at intervals that are appropriate to determine treatment effect with samples for the primary endpoint drawn during Treatment Period 6. Samples will be collected at intervals that are appropriate to determine the uricase activity of SEL-212. Safety will be monitored throughout the study with an independent data safety monitoring board (DSMB).

The study will be divided into 3 study phases: Screening, Treatment, and Follow-up, described below. The study is depicted schematically in [Figure 1](#).

The total duration of participation in the study will range from approximately 26 to 31 weeks (184 to 215 days) as follows:

- Screening and/or washout and premedication Phase: up to 45 days (up to 6.5 weeks)
- Treatment Phase: 168 days (24 weeks)
- Safety Follow-Up: 30 days after last infusion

7.1.1 Screening Phase

After providing written informed consent, the patient is considered enrolled in the study. Patients will be evaluated for inclusion during the Screening Phase. For all patients, the standard Screening Phase will be up to 45 days prior to Baseline. The Screening Phase may be initiated by a preliminary screening with an abbreviated informed consent focused on COVID-19 testing and serum uric acid levels followed by providing study-wide informed consent and the remainder of screening assessments if determined to proceed. **Of note**, if the sUA level obtained during preliminary screening meets eligibility requirements (i.e., ≥ 7 mg/dL), the sUA should **not** be repeated during the subsequent complete screening assessment. Concurrently with the Screening Phase, a premedication period for potential gout flare with colchicine (or non-steroidal anti-inflammatory drug [NSAID], if colchicine is contraindicated) of at least 7 days prior to Baseline will be required for all patients, and a washout period of at least 7 days will be required prior to Baseline for patients on any urate-lowering therapy (ULT). Both the ULT washout

period and the gout flare prophylaxis period may be started earlier than 7 days prior to Baseline. At the discretion of the PI, chronic refractory gout patients whose sUA is lower than the eligibility level of ≥ 7 mg/dL on prescreening or initial screen, may undergo ULT washout prior to retesting the sUA. Initiation of gout flare prophylaxis with colchicine (or non-steroidal anti-inflammatory drug [NSAID], if colchicine is contraindicated) can also be considered coincidentally with the ULT washout to prevent a potential gout flare.

7.1.2 Double Blind Treatment Phase

The total duration of the double-blind Treatment Phase will be approximately 6 months (i.e., 168 days, consisting of six 28-day treatment cycles).

Eligible patients, stratified as to the presence or absence of tophi, will be randomized in a 1:1:1 allocation ratio prior to Baseline to receive one of two dose levels of SEL-212 or placebo. The SEL-212 doses will differ as to the SEL-110.36 component. Participants will receive SEL-037 administered at a dose level of 0.2 mg/kg via intravenous (IV) infusion immediately after receiving SEL-110.36 at a dose level of either 0.1 mg/kg (SEL-212A) or 0.15 mg/kg (SEL-212B) via IV infusion. The placebo will consist of normal saline that will be administered in the same way that the SEL-212 components are administered to maintain the integrity of the study blind. Refer to [Section 10](#) for details about study drug administration.

Patients will complete 6 treatment periods each having a duration of 28 days. Patients will receive treatment with study drug or placebo on Day 0 of each treatment period for a total of 6 doses. For each treatment cycle, patients in both treatment and placebo groups will receive premedication to minimize the potential for infusion reactions during study drug administration. After completing the study drug infusions, participants will remain at the investigational site for 1 hour for safety assessments.

With each dose, a blood sample will be drawn for assessment of sUA level and uricase activity immediately prior to infusion (i.e., Time 0 h) with SEL-212 or placebo and 1 hour after the infusion of the second component of SEL-212 or of placebo is completed. Serum uric acid levels will be assessed through additional post-infusion blood samples at pre-determined time points by an independent, central, unblinded medical monitor.

Gout flares will be assessed at each study visit during the Treatment Phase using a validated definition of flares in patients with established gout ([Gaffo 2018](#)). In addition, in an exploratory manner, gout flares will be self-assessed by the patient weekly after randomization and in each Treatment Period using a weekly flare diary ([Poiley 2016](#)). Patient reported outcome measures (PROs), tophus burden and joint swelling and tenderness will be assessed on Day 0 of Treatment Periods 1 and 4, and at the end of Treatment Period 6 or early termination (ET) if a patient discontinues the study prior to the end of 6 monthly infusions. Samples for anti-uricase, anti-PEG, and anti-pegadricase antibody levels will be taken (i) prior to administration of study drug dosing and at Day 21 for each of the six treatment periods throughout the trial and (ii) at the end of Treatment Period 6 or at ET. Exploratory assessments of inflammatory/immunologic biomarkers and multiomic analysis will also be assessed.

[figure not shown]
Safety laboratory samples, consisting of, but not limited to, complete blood count (CBC) including white blood cell count (WBC) and absolute neutrophil count; liver function tests (LFTs) including aspartate aminotransferase (AST) and alanine transaminase (ALT); serum lipids (including triglycerides and low density lipoprotein (LDL)), analyses of renal function including creatinine, urine albumin creatinine ratio (UACR), and estimated glomerular filtration rate (eGFR) will be collected on Day 0 and Day 21 of Treatment Period 1, on Day 21 only of each of Treatment Periods 2-5, and on Day 21 and Day 28 / ET of Treatment Period 6. On Treatment Period 1 Day 0, safety laboratory samples will be collected pre-infusion in both the SEL-212 arm and the placebo arm. Concomitant medications and procedures and adverse events (AEs) will be monitored continuously during the study. Post-Baseline chest X-rays (CXR) will be taken at six months / ET to assess for presence of or changes in interstitial lung disease (ILD) compared to baseline CXR.

7.1.3 Follow-Up Phase

Patients will be followed for safety monitoring (30 + 4 days) after their final study drug infusion and will have an End of Study visit by telephone at the following times: either (1) at the completion of the 6 month Treatment Phase or (2) at early termination if the patient voluntarily withdraws consent. Patients who terminate the study prematurely will continue to be followed by having all Early Termination assessments performed. Patients who terminate the study prematurely who are unable to be on-site for the Early Termination visit will be contacted by telephone for safety follow-up.

If withdrawn from study drug, regardless of reason, the patient will continue study visits to the end of Treatment Period 6.

Figure 1: Study Schematic

7.2 Number of Patients

The study will randomize approximately 140 patients with chronic refractory gout. Approximately 60% of the randomized patients will have tophi at Baseline.

7.3 Treatment Assignment

Patients will be randomized in a double-blind way with an allocation ratio of 1:1:1 to receive treatment with two different dose levels of SEL-212 or placebo. Randomization will be stratified by presence/absence of tophi.

7.4 Dose Adjustment Criteria

Unless otherwise specified, study drug will be administered as described in [Section 9](#) and [Section 10](#).

7.4.1 Safety Criteria for Adjustment or Stopping Doses

7.4.1.1 SEL-212 or Placebo

A patient will be withdrawn from study drug for meeting the following stopping rule:

- sUA level < 2.0 mg/dL, measured 1 hour after the infusion of the second component of study drug is completed during Treatment Period 1

AND

- sUA level > 1.0 mg/dL measured at the Day 21 visit of Treatment Period 1 or sUA level > 6.0 mg/dL at the Day 21 visit of Treatment Periods 2, 3, 4, or 5

Stopping rules will be assessed by an independent, central, unblinded medical monitor.

If withdrawn from study drug, the patient will continue study visits to the end of Treatment Period 6. The window for all Day 21 visits is +2/-1 days.

If a Day 21 visit sUA value drawn within the protocol window is not available, but if a sUA value drawn at an unscheduled visit after the Day 21 window is available prior to dosing that is \leq 1.0 mg/dL during Treatment Period 1 or \leq 6.0 mg/dL during Treatment Periods 2, 3, 4, or 5, the patient will not be required to be withdrawn from study drug and will be eligible to receive their subsequent dose.

If 1) a Day 21 visit sUA value drawn within the protocol window is not available and no subsequent sUA results are available or 2) a Day 21 visit sUA value drawn within the protocol window is not available and a subsequent sUA drawn at an unscheduled visit after the Day 21 window is > 1.0 mg/dL during Treatment Period 1 or > 6.0 mg/dL during Treatment Periods 2, 3, 4, or 5, then the patient will be withdrawn from study drug based on the protocol deviation. If a protocol deviation occurs where a patient is not able to be dosed within the dosing day window (for example in the case of COVID-19 restrictions temporarily preventing dosing) the current treatment period will be extended up to a maximum of 90 days without skipping doses for patients with a Day 21 visit sUA value \leq 1.0 mg/dL during Treatment Period 1 or \leq 6.0 mg/dL during Treatment Periods 2, 3, 4, or 5 in the D21 visit window or subsequent up to the rescheduled dosing visit. If a protocol deviation occurs in Treatment Period 6 such that the patient was unable to have an EOS visit performed within the visit window, then the Treatment Period 6 Day 28 visit should still occur 28 days (+3/-4 days) after the Treatment Period 6 dose or as close to the visit window as possible to collect the final primary endpoint sUA sample.

To maintain the blind, a central group of unblinded pre-specified medical personnel will adjudicate the implementation of the stopping rules.

If withdrawn from study drug, the patient will continue study visits to the end of Treatment Period 6. At the discretion of the Investigator, the patient will be permitted to return to ULT 60 days after the patient's last study drug treatment. ULT shall not be SEL-212 or any experimental or marketed uricase (e.g., rasburicase (Elitek, Fasturtec), pegloticase (Krystexxa[®])), for the remainder of the study.

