Certain post-dose laboratory results can be unblinding. Therefore, the results of such laboratory tests will be communicated only to unblinded personnel.

Study personnel will endeavor to safeguard the integrity of the study blind to minimize bias in the conduct of the study.

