12.1.8.7 COVID-19 Testing

Patients with COVID-19 infection can experience a range of clinical manifestations, from no symptoms to critical illness.

Screening Visit:

During Screening, all patients should be tested for COVID-19 by an FDA Emergency Use Authorized COVID-19 molecular assay for detection of SARS-CoV-2 RNA. A patient with a positive test result is permitted to request re-testing. A patient who requests re-testing should wait at least 10 days after the date of the first positive COVID-19 diagnostic test, as long as no symptoms have developed. If the second test is positive for COVID-19, then the patient will be excluded from enrollment. If the second test is negative for COVID-19, then the patient must be tested a third time at least 24 hours after the second test to confirm the negative result.

On Study:

Once a patient is enrolled in the study, the investigational site will manage the patient according to its institutional standards and procedures established for COVID-19. During the study, a patient presenting with both symptoms (only severe and critical illness as per definitions below) of COVID-19 and positive COVID-19 test results will be discontinued from study treatment. The patient will be permitted to resume study visits for continued assessments (but not treatment with SEL-212 or placebo) according to the institutional standards and/or procedures of the investigational site.

Patients with mild-moderate COVID-19 illness (as per definitions below) will be allowed to resume study visits (on treatment with SEL-212 or placebo) after resolution of acute symptoms of clinical disease (except for loss of smell and taste) and meeting quarantine requirements so long as their subsequent dose occurs ≤90 days from their prior dosing day as per section 7.4.1.1. Patients with mild-moderate COVID-19 illness can continue **non-dosing study visits** as per protocol mandated visit window prior to resolution of acute symptoms according to the institutional standards and/or procedures of the investigational site.

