Enrolled patients in the study with mild-moderate COVID-19 illness can be treated with anti-SARS-CoV-2 monoclonal antibodies. These patients will be allowed to resume study visits (on treatment with SEL-212 or placebo) after 2 weeks of receiving monoclonal antibodies, and confirmation of resolution of acute symptoms of clinical disease (except for loss of smell and taste), and meeting quarantine requirements so long as their subsequent dose occurs ≤90 days from their prior dosing day as per section 7.4.1.1.

Regardless of COVID-19 disease severity, enrolled patients in the study who are treated for COVID-19 with anti-viral therapy (including Remdesivir), anti-cytokine therapies (including anti-IL-6 or anti-IL-1 therapy), or JAK-inhibitors will be discontinued from study treatment. These patients will be permitted to resume study visits for continued assessments (but not treatment with SEL-212 nor placebo) according to the institutional standards and/or procedures of the investigational site.

The categories of severity of illness (description and criteria) for COVID-19 are noted below as a reference:

Asymptomatic or Pre-symptomatic Infection: Individuals who test positive for COVID-19 but who have no symptoms that are consistent with COVID-19.

Mild Illness: Individuals who have any of the various signs and symptoms of COVID-19 (e.g., fever, cough, sore throat, malaise, headache, muscle pain, nausea, vomiting, diarrhea, loss of taste and smell) but who do not have shortness of breath, dyspnea, or abnormal chest imaging.

Moderate Illness: Individuals who show evidence of lower respiratory disease during clinical assessment or imaging and who have an oxygen saturation (SpO₂) ≥94% on room air at sea level.

Severe Illness: Individuals who have SpO₂ <94% on room air at sea level, a ratio of arterial partial pressure of oxygen to fraction of inspired oxygen (PaO₂/FiO₂) <300 mm Hg, respiratory frequency >30 breaths/min, or lung infiltrates >50%.

Critical Illness: Individuals who have respiratory failure, septic shock, and/or multiple organ dysfunction.

The Investigator will report a patient's positive test results for COVID-19 according to institutional standards and/or procedures.

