5. Study drug dosing to occur 28 days from the previous dose with a window of -4 days to +3 day of the intended dosing day. If a protocol deviation occurs where a patient is not able to be dosed within the dosing day window, for example in the case of COVID-19 restrictions temporarily preventing dosing, the current treatment period will be extended up to a maximum of 90 days without skipping doses for patients with a Day 21 visit sUA value ≤ 1.0 mg/dL during Treatment Period 1 or ≤ 6.0 mg/dL during Treatment Periods 2, 3, 4, or 5 in the D21 visit window or subsequent up to the rescheduled dosing visit. If a protocol deviation occurs in Treatment Period 6 such that the patient was unable to have an EOS visit performed within the visit window, then the Treatment Period 6 Day 28 visit should still occur 28 days (+3/-4 days) after the Treatment Period 6 dose or as close to the visit window as possible to collect the final primary endpoint SUA sample.
6. Assessment performed at select sites only
7. Full physical exam
8. Directed physical exam
9. Assess vital signs on Day 0 at Time 0 (pre-dose), within + 5 minutes after completion of infusion of the first component of study drug, and 1 hour (+ 5 minutes) after completion of infusion of the second component of study drug.
10. Height measured once during Screening only.
11. Screening labs to include: calcium, total complement, hemoglobin-A1c (HbA1c), hepatitis C antibody, hepatitis B surface antigen, human immunodeficiency virus 1/2 (HIV1/2), urinalysis, glucose-6-phosphate dehydrogenase (G6PD)

[figure not shown]
12. Dispense gout flare medication at Screening and as needed during the study. Dispense infusion reaction medication at Screening and at Day 21 of Treatment Periods 1-5.
13. Begin at least 7 days prior to Day 0 of Treatment Period 1.
14. Begin at least 7 days prior to Day 0 of Treatment Period 1.
15. Randomization is permitted at any time between Day -7 to Day 0 (prior to SEL-212 administration).
16. Premedication to minimize potential infusion reactions: oral antihistamines at 12 (\pm 2) hours and 2 (\pm 1) hours and IV steroids at 1 (\pm 0.5) hours prior to study medication.
17. Chemistry labs to include: Alkaline phosphatase, alanine aminotransferase (ALT), aspartate aminotransferase (AST), Total Bilirubin, blood urea nitrogen (BUN), Creatinine, UACR, eGFR, Fibrinogen, Glucose (fasting), Electrolytes (sodium, potassium, chloride, bi-carbonate, phosphate, and magnesium)

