**Statistical Analysis Plan**  
 Sponsor: Selecta Biosciences  
 Protocol No.: SEL-212/302

---

for patients with a Day 21 visit sUA value  $\leq 1.0$  mg/dL during Treatment Period 1 or  $\leq 6.0$  mg/dL during Treatment Periods 2-11 in the D21 visit window or subsequent up to the rescheduled dosing visit. If a protocol deviation occurs in Treatment Period 6 such that the patient was unable to have an EOS visit performed within the visit window, then the Treatment Period 6 Day 28 visit should still occur 28 days (+3/-4 days) after the Treatment Period 6 dose or as close to the visit window as possible to collect the final primary endpoint sUA sample.

To maintain the blind, a central group of unblinded pre-specified medical personnel will adjudicate the implementation of the stopping rules.

If withdrawn from study drug, regardless of reason, the patient will continue study visits including during the follow-up phase.

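### The late-sample rule omits the stopping rule's one-hour sUA condition, so a late Day 21 sample removes placebo patients whom an in-window sample would keep; the expected number is small

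*Protocol*

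**What the plan says.** Protocol 7.4.1.1 sets a two-part stopping rule joined by AND. The first part is sUA below 2.0 mg/dL, "measured 1 hour after the infusion of the second component of study drug is completed during Treatment Period 1". The second is a Day 21 value above 1.0 mg/dL in Period 1 or above 6.0 mg/dL in Periods 2 to 5. The Day 21 window is +2/-1 days.

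Two further situations end in withdrawal when no in-window Day 21 value exists. In case 1 there is no later sUA result either. In case 2 a later unscheduled sample is above the same 1.0 or 6.0 mg/dL threshold. For both, "then the patient will be withdrawn from study drug based on the protocol deviation". A late value at or below the threshold lets the patient continue. The synopsis and SAP 3.3 carry the same rule.

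A delayed dose is covered by a separate clause. The treatment period is "extended up to a maximum of 90 days without skipping doses for patients with a Day 21 visit sUA value" at or below 1.0 or 6.0 mg/dL. Footnote 5 of Appendix A repeats this ("the current treatment period will be extended up to a maximum of 90 days without skipping doses for patients"), as does footnote 5 of SAP Table A. SAP 3.3 gives the range as "Treatment Periods 2-11 in the D21 visit window or subsequent up to the rescheduled dosing visit".

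Section 12.1.8.7 says that patients with mild to moderate COVID-19 "will be allowed to resume study visits (on treatment with SEL-212 or placebo) after resolution of acute symptoms of clinical disease", and repeats this for those given antibody treatment: "These patients will be allowed to resume study visits (on treatment with SEL-212 or placebo) after 2 weeks of receiving monoclonal antibodies". Both sentences require the next dose within 90 days and refer back to 7.4.1.1.

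**The concern.** The one-hour condition is what keeps placebo patients on study drug. Saline should not bring sUA below 2.0 mg/dL, and entry requires at least 7 mg/dL, so a placebo patient will normally exceed the Day 21 threshold at every visit and still be dosed. Case 2 removes that protection. It cannot be read in, because case 2 restates only the Day 21 threshold and gives its own ground for withdrawal.

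Two things are at stake. First, one site error has different consequences by arm. A placebo patient loses the remaining infusions and the steroid and antihistamine premedication that goes with them (10.6.2), and may return to urate-lowering therapy 60 days after the last dose. A controlled SEL-212 patient loses nothing. Second, the site knows that the sample was late and sees whether the patient is dosed again. The protocol restricts laboratory results that could unblind ("Therefore, the results of such laboratory tests will be communicated only to unblinded personnel"), but that hides the value and not the dosing decision. Flares, tender joints, SF-36 and HAQ-DI are key secondary endpoints that knowledge of treatment could affect.

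**Working it through.** **The rules side by side.** Illustrative sUA values in mg/dL:

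| Patient (one-hour value, Day 21 or late value) | In window | Late, as written | Late, one-hour condition added |
|---|---|---|---|
| Placebo (8, 8) | stays | withdrawn | stays |
| SEL-212, controlled (0.2, 0.5) | stays | stays | stays |
| SEL-212, control lost (0.2, 7.5) | withdrawn | withdrawn | withdrawn |

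Lateness changes the outcome only for patients who never met the one-hour condition: in practice placebo, plus any SEL-212 patient whose one-hour value was 2.0 or above (taken as negligible below).

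**Inputs.** From the documents: about 47 patients per arm, 1:1:1 allocation, six doses, five Day 21 decisions, and assumed response of 45% on SEL-212 and 5% on placebo (13.1). With two-sided alpha 2.5%, 90% power and continuity correction, those rates reproduce the plan's 32 per arm, and 35 after 8% dropout. The documents give no rate of missed Day 21 windows and no split between cases 1 and 2. I assume q = 1% or 2% of visits without an in-window value, and a case 2 share s = 50%.

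**Placebo patients affected.**
- Any missed window over five visits: 47 × (1 − (1 − q)^5) = 2.30 at 1%, 4.52 at 2%.
- Case 2 at s = 50%: 1.2 and 2.3. Over s = 25% to 100%: 0.6 to 2.3 at 1%, and 1.1 to 4.5 at 2%.
- Expected doses if every miss led to withdrawal: E = 1 + Σ(1 − q)^k, k = 1 to 5, = 5.852 and 5.708. Doses missed per withdrawn patient: (6 − E)/(1 − (1 − q)^5) = 3.02 and 3.04.
- Doses lost at s = 50%: 0.5 × 47 × (6 − E) = 3.5 and 6.9 of 282, or 1.2% and 2.4%.

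**Strength of the signal.** With 45% of SEL-212 and 5% of placebo patients at or below threshold as stand-ins, and twice as many SEL-212 as placebo patients, the chance that a patient redosed after a late sample is on SEL-212 is 0.90/(0.90 + 0.05) = 94.7%, against 66.7% beforehand. With the one-hour condition added it is 0.90/(0.90 + 1) = 47.4%.

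**How often the signal arises.** Assume that 45% of SEL-212 patients keep control through five Day 21 visits at a constant rate c = 0.45^(1/5) = 0.852, and that no placebo patient falls below threshold.
- At-risk visits in units of one arm: 2 × Σc^(k−1) + 5 = 7.45 + 5 = 12.45; times 47 is about 585 visits.
- Late-sample decisions at s = 50%: 585 × q × 0.5 = 2.9 and 5.9.
- As written, share that are redosings pointing to SEL-212: 0.852 × 7.45/12.45 = 51%, or 1.5 and 3.0 redosings.
- With the condition added, share that are withdrawals pointing to SEL-212: 0.148 × 7.45/12.45 = 8.8%, or 0.3 and 0.5 withdrawals.
- For overall control of 37% to 60%, the shares are 48% to 56% as written and 10% to 6% after the change.

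**For comparison.** Main-rule withdrawals already point to SEL-212, because placebo patients should not meet the rule. Under the same assumption there are 94 × 0.55 = 52 of them (59 to 38 for control of 37% to 60%).

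**Primary endpoint.** Placebo patients withdrawn this way would mostly be non-responders anyway: 1.2 to 2.3 patients × 5% is about 0.06 to 0.1 expected responders.

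**The case against.** The strongest reply is that the wording is a deliberate safety choice: no further uricase without a timely or reassuring sUA. It sits under safety criteria, and Section 5.5 notes that, with the marketed pegylated uricase, infusion reactions are typically preceded by loss of urate lowering. This does not carry the point. The main rule already redoses a patient with a one-hour value of 2.0 or more and a high in-window Day 21 value, the documents give no reason for lateness to change that, and the safety argument has no bearing on saline.

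Other objections stand and limit the weight:
- Day 21 visits and their blood draws may be done remotely (Appendix A, footnote 4), which should keep missed windows uncommon.
- Withdrawn patients continue visits to the end of Period 6, flare prophylaxis continues, and the main estimands of the key secondary endpoints, apart from the sUA responder endpoint in patients with tophi, use treatment policy except for death.
- The protocol is at version 7.1 (December 2022) and the SAP is dated February 2023, so only patients with doses still to come would benefit.

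A reader might also infer that half of late-sample decisions unblinding the site means the trial's blind is broadly lost. The 51% is a share of about 3 to 6 decisions, beside some 52 withdrawals that already reveal the arm. Nor do the documents support reading the 90-day clause as an order to withdraw placebo patients. It states who may be extended and is silent on the rest.

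**Conclusion.** The concern holds as a real but small inconsistency. Case 2 treats late samples by a different rule from in-window ones, and the difference falls almost entirely on placebo. The extension clause leaves placebo patients with no written route to a delayed dose. If 12.1.8.7 imports that filter, its two references to resuming placebo apply to almost no one, so the two sections conflict.

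At the assumed 1% to 2% miss rate and 50% case 2 share, expect about 1 to 2 of 47 placebo patients withdrawn, each missing about three doses, and 1.5 to 3 redosings that point to SEL-212. These counts cover case 2 only; the documents give no basis for counting delayed doses. The effect on the primary endpoint is negligible, and the documents support no direction of bias for the secondary endpoints. The reference to Periods 2 to 11 in SAP 3.3 is a clerical slip: the protocol and footnote 5 of SAP Table A state Periods 2 to 5.

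**What to change.** Add the Period 1 one-hour sUA below 2.0 mg/dL condition to case 2 in the synopsis, Protocol 7.4.1.1 and SAP 3.3. In the same places, and in footnote 5 of both Appendix A and SAP Table A, offer the 90-day extension to any patient who does not meet the full stopping rule. The unblinded medical monitor, who already decides eligibility before each dose in Periods 2 to 6 (10.1), would apply both. Leave case 1 unchanged, since it treats all arms alike, and correct the period range in SAP 3.3 to Periods 2 to 5.

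The cost is a protocol amendment with IRB/IEC approval (15.3) and a SAP wording change, matched in SEL-212/301 if its text is the same. No new assessments are needed. A few SEL-212 patients with a one-hour value of 2.0 or more and a late high value would be redosed, as the main rule already allows in window. Some unblinding remains: a case 2 withdrawal would then point to SEL-212, as main-rule withdrawals already do.
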